4.2.1.2 Dose Modification

Adverse events (both non-serious and serious) associated with Pembrolizumab exposure may represent an immunologic etiology. These adverse events may occur shortly after the first dose or several months after the last dose of treatment. Adverse experiences will be graded and recorded throughout the study and during the follow-up period according to NCI CTCAE Version 4.0. Pembrolizumab must be withheld for drug-related toxicities and severe or life-threatening drug-related AEs as per Table 3 below. See Section 4.6.1 and Events of Clinical Interest Guidance Document for supportive care guidelines, including use of corticosteroids.

**Table 3
Dose Modification Guidelines for Drug-Related Adverse Events**

| Toxicity | Hold Treatment For Grade | Timing for Restarting Treatment | Discontinue Subject |
|----------------------------------|--------------------------|---------------------------------|--|
| Diarrhea/Colitis | 2-3 | Toxicity resolves to Grade 0-1. | Toxicity does not resolve within 12 weeks of last dose or inability to reduce corticosteroid to 10 mg or less of prednisone or equivalent per day within 12 weeks. |
| | 4 | Permanently discontinue | Permanently discontinue |
| AST, ALT, or Increased Bilirubin | 2 | Toxicity resolves to Grade 0-1 | Toxicity does not resolve within 12 weeks of last dose. |

| Toxicity | Hold Treatment For Grade | Timing for Restarting Treatment | Discontinue Subject |
|---|--------------------------|---|--|
| | 3-4 | Permanently discontinue | Permanently discontinue |
| Type 1 diabetes mellitus (if new onset) or Hyperglycemia | T1DM or 3-4 | Hold Pembrolizumab for new onset Type 1 diabetes mellitus or Grade 3-4 hyperglycemia associated with evidence of beta cell failure. | Resume Pembrolizumab when patients are clinically and metabolically stable. |
| Hypophysitis | 2-3 | Toxicity resolves to Grade 0-1 | Toxicity does not resolve within 12 weeks of last dose or inability to reduce corticosteroid to 10 mg or less of prednisone or equivalent per day within 12 weeks. |
| | 4 | Permanently discontinue | Permanently discontinue |
| Hyperthyroidism | 3 | Toxicity resolves to Grade 0-1 | Toxicity does not resolve within 12 weeks of last dose or inability to reduce corticosteroid to 10 mg or less of prednisone or equivalent per day within 12 weeks. |
| | 4 | Permanently discontinue | Permanently discontinue |

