7.3 Stopping Rule for Excess Toxicity

The table displays the stopping rule for excessive toxicity. Excessive toxicity is defined as any drug-related toxicity that results in withholding or discontinuation of pembrolizumab. Additionally, any unexpected grade 3-4 AEs will be defined as excessive toxicity.”

| # Patients | #Toxicities |
|------------|-------------|
| 5 | 3 |
| 10 | 4 |
| 15 | 5 |
| 20 | 7 |
| 25 | 8 |
| 30 | 9 |
| 35 | 10 |

[figure not shown]
The trial is suspended if the number of toxicities is greater than or equal to the number in the second column. For instance, if 5 out of the first 15 patients experience severe toxicity,

the trial is suspended if the number of toxicities is greater than or equal to the number in the second column. For instance, if 5 out of the first 15 patients experience severe toxicity, the trial is suspended.

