7.4 Justification of Design

The plot presents the power of the hypothesis test of the primary efficacy endpoint against the median TTR after *pembrolizumab* treatment. It is seen that 80% power is achieved (at $\alpha=0.1$ in a one-sided test) if the true median TTR is 19.5 months or greater. The stopping rule is based on a beta-binomial probability model that stops the trial if $PP(P(\text{Toxicity}) > 0.2) > 0.8$, where PP is the posterior probability function for $P(\text{Toxicity})$. The posterior model includes a binomial data model and a Beta(2,8) prior for the $P(\text{Toxicity})$. The plot displays the operating characteristics of the rule as a function of the true (unobserved) probability of toxicity. It is seen that, for instance, if the true probability of toxicity is 0.4, the probability the trial will stop early is 0.5, and the expected number of patients accrued is 28.

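### The toxicity stopping rule does not say when a row is read or whether later events count, and its table ends at 35 of the 40 patients, although dosing lasts up to 2 years

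*Combined protocol and SAP*

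**What the plan says.** Section 7.3 pairs numbers of patients with numbers of toxicities: 5/3, 10/4, 15/5, 20/7, 25/8, 30/9 and 35/10. The instruction is "The trial is suspended if the number of toxicities is greater than or equal to the number in the second column", and the worked example is "if 5 out of the first 15 patients experience severe toxicity". The counted event is broad: "Excessive toxicity is defined as any drug-related toxicity that results in withholding or discontinuation of pembrolizumab". Unexpected grade 3–4 events count as well. No observation window, minimum follow-up or reading time is given.

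Section 7.4 supplies the model. "The stopping rule is based on a beta-binomial probability model that stops the trial if" the posterior probability of a toxicity rate above 0.2 exceeds 0.8, and "The posterior model includes a binomial data model and a Beta(2,8) prior". This criterion is not limited to 35 patients.

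The analysis sample in section 7.1 is 40 dosed patients. The Trial Summary gives 18–24 months of enrolment and up to 2 years of pembrolizumab. On timing of toxicity, section 4.2.1.2 says: "These adverse events may occur shortly after the first dose or several months after the last dose of treatment". Adverse events are recorded to 30 days after treatment (section 6.2), and serious ones to 90 days or the start of new anti-cancer therapy, if earlier (section 6.2.3.1).

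**The concern.** A binomial model gives each counted patient a known yes or no. Here the counted event can arise at any cycle, so a patient who has just entered has no settled outcome. With no reading time stated, two teams could follow section 7.3 faithfully and run different rules. One would read row n once, when patient n enters, and count recent entrants as free of toxicity. The other would keep a running count and let later events trigger a row.

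On either reading, the tabled rule has no limit covering patients 36–40. On the first reading, it also ceases to act before accrual closes, while most patients are still early in their possible 2 years of dosing. Safety is one of the two primary objectives, and this is the only numerical safety boundary in the plan.

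**Working it through.** **1. The plan's boundaries.** For r toxicities in n patients the posterior is Beta(2 + r, 8 + n − r). The limit is the smallest r with P(rate > 0.2) > 0.8. This gives 3, 4, 5, 7, 8, 9 and 10 at n = 5, 10, …, 35, so all seven tabled limits reproduce.

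**2. The plan's operating characteristics.** Section 7.4 states that "if the true probability of toxicity is 0.4, the probability the trial will stop early is 0.5". Its mean accrual at that rate is given as 28. An exact sequential binomial calculation over the seven rows, with complete outcomes, gives 0.964 and 12.9 patients. The stated pair does not reproduce. It fits a true rate near 0.25 (0.519 and 27.4). This is a separate discrepancy, and nothing below relies on 0.5 or 28.

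**3. The missing row.** At n = 40:
- r = 11: Beta(13, 37) gives P(rate > 0.2) = 0.834, above 0.8.
- r = 10: Beta(12, 38) gives 0.735, below 0.8.

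The plan's own rule therefore gives 40: 11.

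**4. Effect of that row under a running count.** If late events still count, each row is eventually judged on complete outcomes, so the exact calculation applies.

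| True rate | Rows 5–35 | Rows 5–40 | Difference |
|---|---|---|---|
| 20% | 28.2% | 30.4% | 2.2 points |
| 30% | 74.1% | 78.6% | 4.5 points |
| 40% | 96.35% | 97.84% | 1.5 points |

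**5. Follow-up at the last row.** With even accrual of 40 patients over 18–24 months, mean follow-up when row 35 is reached is about 7.6–10.2 months. Nobody has reached 24 months.

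**6. Effect of the reading time.** The documents give no onset times. *Assumptions:* even accrual over 18 or 24 months; each patient has a counted toxicity with the stated probability; onset is uniform over 3, 6 or 12 months from entry. There were 20,000 simulated trials per setting.
- Once-only: row n is read when patient n enters, rows 5–35.
- Re-evaluated: the section 7.4 posterior is applied at each counted toxicity to all patients dosed so far, from the fifth patient on, and continues after accrual closes.

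The ranges cover the two accrual periods.

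| True rate | Onset over | Once-only | Re-evaluated |
|---|---|---|---|
| 20% | 3 months | 13–16% | 26–29% |
| 20% | 6 months | 6–9% | 20–23% |
| 20% | 12 months | 1–2% | 16–17% |
| 30% | 3 months | 54–59% | 76–78% |
| 30% | 6 months | 36–45% | 72–74% |
| 30% | 12 months | 9–20% | 69–70% |
| 40% | 3 months | 89–91% | 97–98% |
| 40% | 6 months | 76–83% | 97% |
| 40% | 12 months | 35–57% | 97% |

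The re-evaluated figures stay below the 78.6% of step 4 at a 30% rate because recent entrants still enter the denominator before their outcome is known. With slow onset much of this detection comes after accrual: at 30% and 12-month onset, only about 21–36% of trials are suspended by the time the last patient enters.

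**The case against.** The strongest reply is that section 7.3 never says a count is frozen when the n-th patient enters. Its example fits a running count at least as well. On that reading late events in the first 35 patients still trigger suspension, and the loss is only the 1.5 to 4.5 points from the missing row. This stands. The larger losses hold only under the once-only reading, so they show what the ambiguity could cost and do not establish what the plan will do.

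The onset times are also assumed, and the once-only result at a 30% rate moves from 9% to 59% with them. No single value in that range deserves weight.

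There is other oversight. Table 3 governs holds and discontinuation for individual patients. Section 4.10 allows termination for the incidence or severity of adverse reactions. Section 9.5 lets the disease-center board and the monitoring committee, which meets monthly, suspend accrual. A reader might infer that late toxicity would go unnoticed; the documents do not support that. What these provisions lack is a numerical threshold.

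A reader might also infer that the plan promised 96% detection at a 40% rate, or that its stated 0.5 already allows for late onset. Neither follows. The plan states 0.5, describes no delay model, and that figure does not match its own table.

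**Conclusion.** The point holds as an omission in the formal rule. Two parts are certain from the documents: the reading time and the treatment of later events are unstated, and patients 36–40 have no tabled limit. The second costs 4.5 points of suspension probability at a true 30% rate and 1.5 points at 40%, given complete outcomes.

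The first is conditional. If rows are read once at entry, suspension at a 30% rate could be about 9–59% instead of 74%, under uniform onset over 3 to 12 months and 18–24 months of even accrual. It would be wrong to conclude that the rule will miss most late toxicity, because that requires a reading the text does not state.

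**What to change.** 1. Add the row 40: 11 to the table in section 7.3.
2. State that the section 7.4 posterior criterion is re-evaluated at each new counted toxicity, using all counted toxicities among all patients dosed so far, and that this continues after accrual closes to the end of the protocol's adverse-event collection period.
3. Recompute and restate the operating characteristics on that basis, with the assumed onset times shown.

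Using the whole dosed cohort matters. Re-applying row n to the first n patients only would suspend the trial if a third event arose among the first five when 35 had been dosed and no one else was affected. The posterior on 3 of 35 is 0.04. The text should also keep five dosed patients as the first evaluation, as the table does, or accept that the bare criterion is met by 2 of 2 (Beta(4, 8) gives 0.839).

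The cost is a short text change and a rerun of the calculations. The statistical price is more suspensions at an acceptable rate: at a true 20%, about 16–29%, against 1–16% under the once-only reading. With complete observation the added row alone raises that figure from 28% to 30%. The sponsor should weigh the benefit and this price on the same onset assumptions.

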7.4 Justification of Design

The plot presents the power of the hypothesis test of the primary efficacy endpoint against the median TTR after *pembrolizumab* treatment. It is seen that 80% power is achieved (at $\alpha=0.1$ in a one-sided test) if the true median TTR is 19.5 months or greater. The stopping rule is based on a beta-binomial probability model that stops the trial if $PP(P(\text{Toxicity}) > 0.2) > 0.8$, where PP is the posterior probability function for $P(\text{Toxicity})$. The posterior model includes a binomial data model and a Beta(2,8) prior for the $P(\text{Toxicity})$. The plot displays the operating characteristics of the rule as a function of the true (unobserved) probability of toxicity. It is seen that, for instance, if the true probability of toxicity is 0.4, the probability the trial will stop early is 0.5, and the expected number of patients accrued is 28.

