7.0 STATISTICAL ANALYSIS PLAN

7.1 Analysis Samples

For both the primary safety and efficacy endpoints, the analysis sample will be eligible patients who have taken at least one dose of pembrolizumab. Patients who are eligible but withdraw prior to taking the first dose will not be included in these analyses and will be replaced, so that, barring early stopping, the analysis sample will be 40 patients who have taken at least one dose of drug.

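### The stated behaviour of the toxicity stopping rule is wrong: at a true toxicity rate of 0.4 the tabulated rule stops with probability 0.96 after about 13 patients, not 0.5 after 28

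*Combined protocol and SAP*

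**What the plan says.** Section 7.3 tabulates boundaries at seven looks: 3 toxicities in 5 patients, 4 in 10, 5 in 15, 7 in 20, 8 in 25, 9 in 30 and 10 in 35. The direction is explicit: "The trial is suspended if the number of toxicities is greater than or equal to the number in the second column". The worked example, "if 5 out of the first 15 patients experience severe toxicity", agrees with the 15-patient row.

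Section 7.4 gives the origin of the table. "The stopping rule is based on a beta-binomial probability model that stops the trial if" the posterior probability that the toxicity rate exceeds 0.2 is itself above 0.8. "The posterior model includes a binomial data model and a Beta(2,8) prior for the" toxicity probability. The same paragraph then illustrates the rule's behaviour from a plot. On early stopping it reads: "true probability of toxicity is 0.4, the probability the trial will stop early is 0.5". On accrual it adds that "the expected number of patients accrued is 28".

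Section 7.1 sets the maximum: "barring early stopping, the analysis sample will be 40 patients who have taken at least one dose of drug".

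**The concern.** A rate of 0.4 is twice the 0.2 threshold that the rule is built to detect. The boundary as a proportion of patients falls from 60% at the first look to 29% (10/35) at the last. A true rate of 40% lies at or above that proportion from the second look onwards, so a stopping probability of only one half is implausible on its face.

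The sentence matters because it is the only written statement of how the safety rule performs. An IRB or safety committee relying on it would conclude that 40% toxicity goes unflagged half the time, with about 28 patients accrued on average. It would also have no idea how often the rule stops when toxicity is nearer 20%, and that bears on whether the trial reaches its 40-patient analysis.

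**Working it through.** **Inputs.** Boundaries and the at-or-above direction: section 7.3. Beta(2,8) prior, binomial data, threshold 0.2 and cut-off 0.8: section 7.4. Maximum of 40 treated patients: section 7.1.

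**Step 1: reproduce the boundaries.** With x toxicities in n patients the posterior is Beta(2+x, 8+n−x). The rule stops if 1 − F(0.2; 2+x, 8+n−x) > 0.8, where F is the Beta distribution function.

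| n | Boundary x | Posterior at x | Posterior at x−1 |
|---|---|---|---|
| 5 | 3 | 0.870 | 0.698 |
| 10 | 4 | 0.837 | 0.673 |
| 15 | 5 | 0.811 | 0.656 |
| 20 | 7 | 0.892 | 0.790 |
| 25 | 8 | 0.875 | 0.773 |
| 30 | 9 | 0.859 | 0.759 |
| 35 | 10 | 0.846 | 0.746 |

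Every tabulated x is the smallest count that exceeds 0.8. The table is the stated model, so any discrepancy lies in the illustration.

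**Step 2: a bound that needs no sequential calculation.** If at least 10 of the first 35 patients have a toxicity, the trial has stopped by the 35-patient look at the latest. With X ~ Binomial(35, 0.4), P(X ≥ 10) = 0.942. The stopping probability at 0.4 is therefore at least 0.94.

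**Step 3: exact calculation at a true rate of 0.4.** Start with zero toxicities, add Binomial(5, 0.4) at each look, remove the probability at or above the boundary, and carry the rest forward.

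| Look | P(stop here) | Cumulative |
|---|---|---|
| 5 | 0.317 | 0.317 |
| 10 | 0.318 | 0.636 |
| 15 | 0.173 | 0.808 |
| 20 | 0.038 | 0.847 |
| 25 | 0.054 | 0.901 |
| 30 | 0.039 | 0.939 |
| 35 | 0.024 | 0.964 |

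E[N] = Σ n·P(stop at n) + 40·P(no stop) = 5(0.317) + 10(0.318) + 15(0.173) + 20(0.038) + 25(0.054) + 30(0.039) + 35(0.024) + 40(0.036) = 12.9.

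A simulation of 400,000 trials gave 0.964 and 12.9, with a median of 10 patients. The first two looks alone already give 0.64.

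**Step 4: other true rates, same recursion.**

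| True rate | P(stop) | E[N] |
|---|---|---|
| 0.10 | 0.025 | 39.3 |
| 0.15 | 0.108 | 37.1 |
| 0.20 | 0.282 | 33.0 |
| 0.25 | 0.519 | 27.4 |
| 0.30 | 0.741 | 21.6 |
| 0.35 | 0.890 | 16.6 |
| 0.40 | 0.964 | 12.9 |
| 0.50 | 0.998 | 8.8 |

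Solving P(stop) = 0.5 gives a rate of 0.246. Solving E[N] = 28 gives 0.245. Both printed figures therefore point to almost the same rate, and it is not 0.4.

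**Step 5: other readings at 0.4.** Stopping only when the count exceeds the boundary gives 0.912 and 18.5. Monitoring after every patient gives 0.982 and 10.2. Omitting the look at 5 patients gives 0.963 and 14.7. None gives 0.5 and 28. Raising the toxicity threshold to 0.3 under the same prior comes near (0.553 and 28.6), but that is a different rule with different boundaries, and it contradicts both the table and the model.

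**The case against.** The arithmetic cannot be defended; the case on the other side concerns weight and remedy.

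- **Nothing operative depends on the sentence.** The table, the direction of the boundary, the worked example, the prior and the cut-off all agree. A committee applying the table acts the same way before and after the correction, and the error understates protection at 40% toxicity. This stands as a limit on the consequences, but it does not make the stated figures true.
- **The plot is not available in the text reviewed.** It may be correct, with only one point misread or mistyped. This stands: whether the plot is wrong is unknown. Re-running it from the table settles the question at little cost.
- **The threat to the 40-patient analysis is conditional.** At true rates of 0.10 and 0.15 the rule stops with probability only 0.025 and 0.108. The plan gives no expected rate for this composite event. The nearest figures in section 3.1.2 are 4.2% discontinuing for a related event and 11% with grade 3–5 drug-related events in melanoma, and neither counts withheld doses. Section 7.3 also says the trial is suspended, which need not end it. All of this stands.
- **An expected 13 patients assumes immediate outcomes.** Toxicity includes withholding or discontinuation during up to two years of treatment. If accrual continues while outcomes are pending, more than 13 will be enrolled. This also stands, but the plan's own binomial illustration carries the same assumption, so it does not explain 0.5 and 28.

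**Conclusion.** The concern holds. At a true toxicity rate of 0.4 the rule as tabulated stops with probability 0.96 and an expected 12.9 patients. The stated 0.5 and 28 are out by 0.46 and about 15 patients. The boundaries are consistent with their stated model, so the error is confined to the illustration in section 7.4 and possibly the plot behind it.

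The result assumes looks at 5, 10, …, 35 patients, independent toxicities with a common rate, each patient's toxicity status known at the look, and suspension counted as stopping. That 0.4 was written in place of about 0.25 is a plausible inference, since both printed figures fit that rate, but the mismatch does not depend on it.

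**What to change.** In section 7.4, either keep the rate of 0.4 and give 0.96 for the probability of stopping early and 13 for the expected number accrued, or keep 0.5 and 28 and change the rate to about 0.25. The sponsor should go back to its own calculation to see which was meant.

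Regenerate the operating-characteristics plot from the tabulated boundaries, or confirm that the existing plot matches them. State the stopping probability of 0.28 at a true rate of exactly 0.2, so that readers can see how the rule behaves at its own threshold. Add that the figures assume toxicity status is known at each look and that suspension counts as stopping.

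The cost is one corrected sentence, one added line and a re-run plot. The stopping rule, sample size and analyses are unchanged.

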8.0 LABELING, PACKAGING, STORAGE AND RETURN OF CLINICAL SUPPLIES

8.1 Investigational Product

The investigator shall take responsibility for and shall take all steps to maintain appropriate records and ensure appropriate supply, storage, handling, distribution and usage of investigational product in accordance with the protocol and any applicable laws and regulations.

Clinical Supplies will be provided by Merck as summarized in Table 11.

Table 11 Product Descriptions

| Product Name & Potency | Dosage Form |
|-----------------------------------|----------------------------------|
| pembrolizumab 50 mg | Lyophilized Powder for Injection |
| pembrolizumab 100 mg/ 4mL | Solution for Injection |

8.2 Packaging and Labeling Information

Clinical supplies will be affixed with a clinical label in accordance with regulatory requirements.

8.3 Clinical Supplies Disclosure

This trial is open-label; therefore, the subject, the trial site personnel, the Investigator and/or designee are not blinded to treatment. Drug identity (name, strength) is included in the label text; random code/disclosure envelopes or lists are not provided.

8.4 Storage and Handling Requirements

Clinical supplies must be stored in a secure, limited-access location under the storage conditions specified on the label.

Receipt and dispensing of trial medication must be recorded by an authorized person at the trial site.

Clinical supplies may not be used for any purpose other than that stated in the protocol.

8.5 Returns and Reconciliation

The investigator is responsible for keeping accurate records of the clinical supplies received from Merck or designee, the amount dispensed to and returned by the subjects and the amount remaining at the conclusion of the trial.

Upon completion or termination of the study, all unused and/or partially used investigational product will be destroyed at the site per institutional policy. It is the Investigator's responsibility to arrange for disposal of all empty containers, provided that procedures for proper disposal

have been established according to applicable federal, state, local and institutional guidelines and procedures, and provided that appropriate records of disposal are kept.

